TB, HIV, HepB, Hep C Ab, Anti-CCP, Anti-dsDNA, RF	X															
FSH & estradiol (if applicable)	X															
Serum pregnancy test (WCBP only)	X															
Urine pregnancy test (WCBP only) 		X 	X	X		X		X 		X		X		X	X	X
Haematology, chemistry, urinalysis	X	X 	X	X		X 		X 		X 		X 		X	X	X
CRP	X	X 		X		X		X 		X		X		X	X	
Blood sample for PD inflammatory biomarkers, mRNA, and TE 		X 						X 						X	X	
PK blood samples GSK2982772 		X	X 					X 						X	X	
PK blood samples for MTX 		X 	X 					X 								
Pharmacogenetic sample (PGx)		X 														
Synovial biopsies for PK, inflammatory biomarkers, mRNA, target engagement & pathway engagement analysis 		X 						X 							X 	

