**Footnotes:**

1. Full medical history (includes past and current conditions, medication history, substance usage, and family history of premature CV disease).
2. Full physical exam (includes height/weight at screening, height not measured at later time points).
3. Triplicate ECG to be performed at screening only.
4. Pre-dose.
5. Any SAEs assessed as related to study participation (e.g., protocol-mandated procedures, invasive tests, or change in existing therapy) or related to a GSK product will be recorded from the time a subject consents to participate in the study up to and including any follow-up. AEs will be collected from the start of Study Treatment until the follow-up contact. On Days 22, 36, 50, 64, and 78, subjects will be questioned about their general health status via phone call.
6. All PRO assessments should be conducted on site before any tests, procedures, or assessments, to avoid influencing the subjects' perception.
7. DCE-MRI will be performed on all subjects, provided that sites have DCE-MRI capability and experience (e.g., hardware and software requirements). If sites do not have DCE-MRI capability or experience, a regular MRI will be performed of the affected hand/wrist. If the same joint is used for MRI and synovial biopsy, MRI should be performed before biopsy (if applicable).
8. Subjects must take study medication three times a day approximately 8 hours apart. Exact time of dosing to be recorded in diary cards. On Day 1, the first study dose will be administered at the site. On Days 8, 43 and 85 only, subjects must not take their medication at home in the morning. Subjects will complete pre-dose assessments and then will be administered their morning dose of medication at site on Days 8 and 43. On Day 85, subjects are no longer receiving study medication.
9. If urine pregnancy test is positive, a confirmatory serum pregnancy test must be performed.
10. Haematology and chemistry only. No urinalysis required on Days 29, 57 and 71. When clinical laboratory samples are taken on the same day as the MRI, the samples should be taken first prior to the administration of the contrast fluid with MRI. If this is not feasible (i.e. MRI is performed first), it is recommended that a separate IV catheter or straight venipuncture be performed in the *opposite* arm to where the MRI contrast fluid was administered.

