11. Blood samples for inflammatory biomarkers, mRNA and target engagement. See laboratory manual for full details on sample collection, handling and shipment.
12. PK blood samples for GSK2982772 will be taken pre-dose on Days 8 and 43. Post-dose serial PK samples will be taken on Days 1, 8 and Day 43 at the following time points: 1, 2, 4, and 6 hours. A trough PK sample will be taken on Day 85 or at Early Withdrawal.
13. Only applicable if subjects are on MTX: PK blood samples for MTX will be taken pre-dose GSK2982772 on Day 1 (MTX alone), on Days 8 and 43 (MTX + GSK2982772). Subjects who are on MTX should ideally take their MTX dose on the same day of the week at approximately the same time of the day throughout the study. In addition, the Day 1, 8 and 43 visits should ideally be on the same day of the week.
14. A PGx blood sample is collected at the baseline visit, after the subject has been randomised and provided informed consent for genetic research. If the sample is not collected at the baseline visit, it can be collected at any time during the study after randomisation.
15. Synovial biopsies are optional.
16. Biopsy (if applicable) and MRI only are required at Early Withdrawal visit if subject withdraws after at least 14 days of treatment and prior to Day 43. If a subject withdraws between Days 43 and 57, an MRI is not required at the Early Withdrawal visit. If a subject withdraws on Day 57 or after, an MRI should be performed at the Early Withdrawal visit. A window allowance of  $\pm 3$  days of Early Withdrawal visit is allowed to perform the MRI.
17. Visit windows during the treatment period are relative to Day 1.
18. If a subject withdraws from the study, every effort will be made for the subject to complete an Early Withdrawal visit prior to the Follow Up visit.
19. Follow-up visit should be completed 28 days ( $\pm 3$  days) after the last dose of study medication.
20. MRI (and if applicable; a biopsy) may be performed during the screening window as an additional visit (if required) up to 7 days before Day 1 to allow sites flexibility in scheduling. The MRI must be completed prior to synovial biopsy (if performed on the same joint). The site should be reasonably confident that the subject has fully qualified for the study (e.g., screening clinical labs, vital signs, physical examination, etc.) before the MRI (and if applicable: a biopsy) is/are performed.

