**Table 3 Protocol Required Safety Laboratory Assessments**

Laboratory Assessments	Parameters			
Haematology 	Platelet Count	RBC Indices:	WBC count with Differential:	
	RBC Count	MCV	Neutrophils	
	Hemoglobin	MCH	Lymphocytes	
	Hematocrit		Monocytes	
			Eosinophils	
			Basophils	
Clinical Chemistry 	BUN	Potassium	AST (SGOT)	Total and direct bilirubin
	Creatinine	Sodium	ALT (SGPT)	Total Protein
	Glucose 	Calcium	Alkaline phosphatase	Albumin
	CRP	Triglycerides 	Total Cholesterol 	Fasting HDL cholesterol 
	Fasting LDL cholesterol 			
Routine Urinalysis	
 
• Specific gravity
 
• pH, glucose, protein, blood and ketones by dipstick
 
• Microscopic examination (if blood or protein is abnormal)
 
			
Other Screening and Routine Tests	
 
• HIV 1 & 2
 
• Hepatitis B (HBsAg)
 
• Hepatitis B core antibody (HBcAb)
 
• Hepatitis C (Hep C antibody)
 
• QuantiFeron Gold Test
 
• T-spot (if QuantiFeron is indeterminate)
 
• FSH and estradiol (as needed in women of non-child bearing potential only)
 
• Urine hCG Pregnancy test (as needed for women of child bearing potential)
 
• Serum hCG (as needed for women of child bearing potential) to be done at screening and if urine test positive at other time points in the study.
 
• Anti-dsDNA
 
• Rheumatoid Factor
 
• Anti-CCP
 
• Estimated glomerular filtration rate (eGFR) will be calculated using the CKD-EPI formula.
 
			

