**Footnotes:**

1. The subject's CBC results from the previous scheduled visit should be checked prior to the synovial biopsy procedures according to local practices and may be repeated at the discretion of the investigator.

2. Details of Haematologic Stopping Criteria are given in Section 5.4.5.
3. Details of Liver Chemistry Stopping Criteria and Required Actions and Follow-Up Assessments after liver stopping or monitoring event are given in Section 5.4.3 and Appendix 2.
4. No fasting required. Any abnormal result for glucose or lipids (non-fasted) may be repeated at the discretion of the Investigator.
5. Local urine testing will be standard for the protocol unless serum testing is required by local regulation or ethics committee.

All laboratory tests with values that are considered clinically significantly abnormal during participation in the study should be repeated until the values return to normal or baseline. If such values do not return to normal within a period judged reasonable by the Investigator, the etiology should be identified and the sponsor notified.

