### **7.6.1. Magnetic Resonance Imaging (MRI) of Joint**

The most affected hand will be documented at baseline and used for all imaging visits. If subjects report both hands are equally involved, then the subject's dominant hand will be used.

DCE-MRI will be performed on all subjects, provided that sites have DCE-MRI capability and experience (e.g., hardware and software requirements). If sites do not have DCE-MRI capability, only a standard MRI will be performed.

Each subject's most affected wrist (corresponding to the affected hand which is determined and documented at baseline) will be imaged by MRI at pre-dose on Days 1, 43 and 85 (see Section 7.1). If a scanning failure occurs at any visit, if feasible a rescan

is allowed within 7 days after the failed scan after consultation and agreement with the GSK Medical Monitor. There will be a minimum of 24 hours between scans where gadolinium (Gd) contrast is used. The MRI will be used in order to non-invasively quantify the degree of inflammation and structural changes within the target joint.

Each MRI total scan time should be approximately 1 hour. For each subject, MRIs must be performed on the same scanner and using the same type of chelated Gd contrast agent as was used at screening. If scanning cannot occur on the same scanner within the visit time window due to hardware failure, an alternate scanner may be used or the time window may be extended by 3 days only after consultation and agreement with the GSK medical monitor.

On attendance at the MRI department, subjects will be placed in the scanner and will be prepared for intravenous contrast agent administration. The scanning protocol will include routine localizers, T1 measurement sequences, dynamic DCE-MRI acquisition, and acquisitions required for OMERACT RAMRIS, RAMRIQ and CARLOS scoring. Additional exploratory MRI endpoints, as detailed in the Acquisition Manual, may also be acquired for exploratory purposes.

Details of scanning site training procedures, acceptable Gd contrast agents, and scanning protocols will be provided in a dedicated Imaging Manual.

All MRI scans will be reported at the site by a radiologist (non-anonymized) for clinical abnormalities.

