#### 9.2.1. Sample Size Assumptions

The study is not powered to detect pre-defined differences. A sufficient number of subjects will be screened so that approximately 24 subjects with moderate to severe RA are randomised into the study on a TID regimen. Prior to protocol amendment 3 being approved in each country, no more than 18 subjects will be randomised into the study on a BID regimen. [Table 4](#) summarises the total planned sample sizes for BID and TID regimens. Should the drop-out rate be higher than anticipated, additional or replacement subjects may be randomised (up to an overall total maximum of 48) into the study at the discretion of the Sponsor.

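### The optional early baseline MRI (Section 7.1, footnote 20) has no pregnancy test attached, so gadolinium can be given on a screening test that is 23 to 29 days old

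*Protocol*

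**What the plan says.** Section 7.6.1 states that the affected wrist "will be imaged by MRI at pre-dose on Days 1, 43 and 85", and describes preparing the subject for intravenous contrast as part of the scan. Footnote 20 to the Time and Events Table (Section 7.1) relaxes the baseline timing: the MRI, with a biopsy where applicable, "may be performed during the screening window as an additional visit (if required) up to 7 days before Day 1". It attaches one condition on readiness: "The site should be reasonably confident that the subject has fully qualified for the study", with screening laboratory results, vital signs and physical examination as examples.

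The extra visit has no column of its own in the table. The serum pregnancy test is marked in the Screening column only. The row headed "Urine pregnancy test (WCBP only)" is first marked on Day 1, before dosing, and then at every later site visit. Table 3 in Section 7.3.6 agrees: "Serum hCG (as needed for women of child bearing potential) to be done at screening", or to confirm a positive urine test. It lists the urine test as one to be done when needed. The Screening column allows up to 30 days before Day 1.

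**The concern.** When the baseline scan takes place on Day 1, it shares a visit with a scheduled urine pregnancy test. Footnote 20 lets the scan move ahead of that visit but moves no test with it. A site that follows the schedule exactly can then give gadolinium to a woman of childbearing potential on the strength of a screening result that may be several weeks old. The next required test falls after the exposure, when it can no longer prevent it.

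Two residual cases are at stake: a conception too recent for the screening serum test to detect, and a contraceptive failure between screening and the early scan. The hazard itself is limited. The gadolinium row of the risk table in the appended original protocol (Section 4.6.1) refers to reproductive toxicity in animals at repeated high doses, and caps contrast at 0.1 mmol/kg per imaging session. Only the baseline scan, one of three planned, is concerned.

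**Working it through.** The plan gives no figure on this point, so there is nothing to reproduce. The check is a day count followed by a rough estimate of expected cases.

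**Inputs from the Protocol**
- Screening: up to 30 days before Day 1 (Section 7.1, Screening column).
- Early baseline MRI: up to 7 days before Day 1, so 7 to 1 days before (footnote 20).
- Required pregnancy tests up to Day 1: serum at Screening, urine before dosing on Day 1 (Section 7.1; Table 3).
- Number of subjects: "approximately 24 subjects with moderate to severe RA are randomised into the study on a TID regimen" (Section 9.2.1).

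**Assumptions, not taken from the Protocol**
- Screening 21 or 14 days before Day 1, as milder examples.
- A contraceptive failure rate of 1% per year.
- 24 women of childbearing potential as an extreme, 12 as a less extreme case, all using the early visit.

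**Step 1: age of the last required test at contrast**

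Age = (days from screening to Day 1) − (days from MRI to Day 1).

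| Screening before Day 1 | MRI 7 days before | MRI 1 day before |
|---|---|---|
| 30 days (limit) | 30 − 7 = 23 days | 30 − 1 = 29 days |
| 21 days (assumed) | 21 − 7 = 14 days | 21 − 1 = 20 days |
| 14 days (assumed) | 14 − 7 = 7 days | 14 − 1 = 13 days |

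**Step 2: time from contrast to the next required test**

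That test is the Day 1 urine test, so the delay equals the lead time of the scan: 7 days down to 1 day.

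**Step 3: expected contraceptive-failure pregnancies between screening and scan, screening at the 30-day limit**

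Expected number = women × annual failure rate × days / 365.

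- 24 women: 24 × 0.01 × 23/365 = 0.0151, to 24 × 0.01 × 29/365 = 0.0191.
- 12 women: 12 × 0.01 × 23/365 = 0.0076, to 12 × 0.01 × 29/365 = 0.0095.

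The result is proportional to the assumed rate. At twice the rate (2% per year) the figures for 24 women become 2 × 0.0151 = 0.030 to 2 × 0.0191 = 0.038. None of these figures counts conceptions just before screening that the serum test would miss.

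**The case against.** The strongest reply is that several protections are already in place. A negative serum test is a condition of eligibility for female subjects; it appears in the appended original Section 5.1 and in the Amendment 3 change list. Footnote 20 points the site back to the screening results before it scans. The appended original text requires contraception from 30 days before the first dose, which covers the whole screening window, and excludes anyone with a contraindication to gadolinium under local guidelines. Table 3 lets a site repeat the urine test when needed. The Imaging Manual and the current Section 4.6.1, where a check before contrast could sit, are not shown. All of this stands, and it is why the point is small. None of it, as far as the text can be seen, requires a test between screening and the early scan.

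Two stronger readings are tempting, and the documents do not support either.

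- A reader might infer that contrast can be given at baseline with no negative test required at all. That is not so, because the screening serum test is required and must be negative. The issue is how old the result can be.
- A reader might infer from footnote 10, which contains the words "If this is not feasible (i.e. MRI is performed first", that the scan may also precede the urine test on Day 1. Footnote 10 marks the haematology and chemistry cells on Days 29, 57 and 71. It concerns blood draws and which arm to use, and its default is samples before contrast. It says nothing about the order of the Day 1 urine test.

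It may also be said that Appendix 6 supplies the failure rate used above. Its criterion of less than 1% per year stands in the part on partners of male subjects, and the list for female subjects states no rate. The 1% is therefore a plain assumption here.

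**Conclusion.** The gap is real but minor. For women of childbearing potential scanned at the optional early visit, no visible text requires a pregnancy test after Screening and before contrast. The worst-case test age of 23 to 29 days needs screening at the 30-day limit and is shorter otherwise.

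The expected number of cases is very small: about 0.015 to 0.019 if every one of about 24 TID subjects were a woman of childbearing potential, used the early visit, and was screened at the limit, at an assumed failure rate of 1% per year. It would be smaller in practice if fewer women used the visit or were screened later.

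This is a point of safety scheduling, and it does not affect any statistical result. Since the current Section 4.6.1 and the Imaging Manual are not available, no contradiction with them is claimed. If either already requires a test before contrast, footnote 20 only needs a cross-reference. The change is worth making because it is cheap.

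**What to change.** Add one sentence to footnote 20: for women of childbearing potential, a negative local urine pregnancy test is required on the day of an early baseline MRI, before contrast is given. Keep the Day 1 pre-dose urine test as it is.

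This reduces the interval between the last required test and contrast from as much as 29 days to 0. It will not detect a conception too recent for any test to show, but it does cover most of the interval that is now untested.

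The cost is one extra urine test for each woman who uses the optional visit. No new method is needed, since Table 3, footnote 5, already provides that "Local urine testing will be standard for the protocol unless serum testing is required by local regulation or ethics committee".

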## 7.2. Screening and Critical Baseline Assessments

After written informed consent, screening assessments will be performed as outlined in the Time and Events Table (Section 7.1).

The following demographic parameters will be captured: year of birth, sex, race and ethnicity.

Medical/medication/mental health and family history, ECG and laboratory tests will be assessed as related to the inclusion/exclusion criteria listed in Section 5.

Cardiovascular medical history/risk factors and smoking history (as detailed in the CRF) will be assessed at screening.

Patient Reported Outcomes questionnaires should be completed by subjects before any other assessment at a clinic visit, in the order specified in the SRM.

## 7.3. Safety

Planned time points for all safety assessments are listed in the Time and Events Table (Section 7.1). Additional time points for safety tests (such as vital signs, physical exams and laboratory safety tests) may be added during the course of the study based on newly available data to ensure appropriate safety monitoring.

The Investigator will be responsible for determining the clinical significance of any results that fall outside of the laboratory normal ranges.

In line with routine pharmacovigilance, an internal GSK Safety Review Team (SRT), which will include 203168 study team members, will review blinded safety data, including clinical laboratory parameters and adverse events, at appropriate intervals during the period of study conduct.

### 7.3.1. Adverse Events (AEs) and Serious Adverse Events (SAEs)

The definitions of an AE or SAE can be found in [Appendix 5](#).

The Investigator and their designees are responsible for detecting, documenting and reporting events that meet the definition of an AE or SAE.

#### 7.3.1.1. Time period and Frequency for collecting AE and SAE information

- Any SAEs assessed as related to study participation (e.g., protocol-mandated procedures, invasive tests, or change in existing therapy) or related to a GSK product will be recorded from the time a subject consents to participate in the study up to and including any follow-up contact.
- AEs will be collected from the start of Study Treatment until the follow-up contact (see Section 7.3.1.3), at the time points specified in the Time and Events Table (Section 7.1).

- Medical occurrences that begin prior to the start of study treatment but after obtaining informed consent may be recorded on the Medical History/Current Medical Conditions section of the CRF.
- All SAEs will be recorded and reported to GSK within 24 hours, as indicated in [Appendix 5](#).
- Investigators are not obligated to actively seek AEs or SAEs in former study subjects. However, if the Investigator learns of any SAE, including a death, at any time after a subject has been discharged from the study, and he/she considers the event reasonably related to the study treatment or study participation, the Investigator must promptly notify GSK.

NOTE: The method of recording, evaluating and assessing causality of AEs and SAEs plus procedures for completing and transmitting SAE reports to GSK are provided in [Appendix 5](#).

#### **7.3.1.2. Method of Detecting AEs and SAEs**

Care will be taken not to introduce bias when detecting AEs and/or SAEs. Open-ended and non-leading verbal questioning of the subject is the preferred method to inquire about AE occurrence. Appropriate questions include:

- “How are you feeling?”
- “Have you had any (other) medical problems since your last visit/contact?”
- “Have you taken any new medicines, other than those provided in this study, since your last visit/contact?”

#### **7.3.1.3. Follow-up of AEs and SAEs**

After the initial AE/SAE report, the Investigator is required to proactively follow each subject at subsequent visits/contacts. All SAEs, and non-serious AEs of special interest (as defined in Section 4.6.1) will be followed until resolution, until the condition stabilizes, until the event is otherwise explained, or until the subject is lost to follow-up (as defined in Section 5.4). Further information on follow-up procedures is given in [Appendix 5](#).

#### **7.3.1.4. Cardiovascular and Death Events**

For any cardiovascular events detailed in [Appendix 5](#) and all deaths, whether or not they are considered SAEs, specific Cardiovascular (CV) and Death sections of the CRF will be required to be completed. These sections include questions regarding cardiovascular (including sudden cardiac death) and non-cardiovascular death.

The CV CRFs are presented as queries in response to reporting of certain CV MedDRA terms. The CV information should be recorded in the specific cardiovascular section of the CRF within one week of receipt of a CV Event data query prompting its completion.

The Death CRF is provided immediately after the occurrence or outcome of death is reported. Initial and follow-up reports regarding death must be completed within one week of when the death is reported.

#### **7.3.1.5. Regulatory Reporting Requirements for SAEs**

Prompt notification by the Investigator to GSK of SAEs related to study treatment (even for non- interventional post-marketing studies) is essential so that legal obligations and ethical responsibilities towards the safety of subjects and the safety of a product under clinical investigation are met.

GSK has a legal responsibility to notify both the local regulatory authority and other regulatory agencies about the safety of a product under clinical investigation. GSK will comply with country specific regulatory requirements relating to safety reporting to the regulatory authority, Institutional Review Board (IRB)/Independent Ethics Committee (IEC) and Investigators.

Investigator safety reports are prepared for suspected unexpected serious adverse reactions according to local regulatory requirements and GSK policy and are forwarded to Investigators as necessary.

An Investigator who receives an Investigator safety report describing a SAE(s) or other specific safety information (e.g., summary or listing of SAEs) from GSK will file it with the IB and will notify the IRB/IEC, if appropriate according to local requirements.

